10.2 Serious Adverse Events

10.2.1 Definition of a Serious Adverse Event

An adverse event or suspected adverse reaction is considered ‘serious’ if, in the view of the investigator, it results in any of the following outcomes:

- (a) Death;
- (b) Is life threatening;
- (c) Results in persistent or significant incapacity or substantial disruption of the ability to conduct normal life functions;
- (d) A congenital anomaly/birth defect;
- (e) Requires in-participant hospitalization or prolongs an existing hospitalization;
- (f) An important medical event that may jeopardize the participant or participant and may require medical or surgical intervention to prevent one of the outcomes listed above.

10.2.2 Serious Adverse Events (SAE) Classifications Common in Severe AH

Acute kidney injury:

- Increase in creatinine of 50% above baseline over a period of 7 days
- Increase in creatinine of 0.3 mg/dl within a period of 48 hrs.
- Onset of renal failure requiring dialysis

Sepsis:

- Life-threatening organ dysfunction caused by a dysregulated host response to infection
- An increase in SOFA score of 2 points or more
- Note: most participants with severe AH have 4 points based on bilirubin only

Infection:

- Pneumonia defined as new infiltrate by CXR or Chest CT scan not explained by “fluid overload”
- Positive blood cultures for bacteria or fungus, not suspected as contaminant
- Positive urine fungal culture > 50,000 colonies/ml
- Positive urine bacterial culture > 100,000 colonies/ml (mixed flora is excluded)
- Soft tissue or bone infections including cellulitis or abscess documented by exam or scan
- CNS infection defined as positive culture of CSF or > 5 WBC/ml
- Ascitic fluid white cell count > 500/ml or neutrophils > 250/ml. with or without positive bacterial or fungal cultures

Decompensation of liver disease:

- New onset of ascites if not present on admission to study
- New onset of variceal hemorrhage
- New onset of hepatic encephalopathy (HE).

Hepatic failure defined as increase in MELD score ≥ 5 on two consecutive occasions

Cerebral failure defined as worsening HE \geq Grade 3 if hepatic encephalopathy present on admission

Renal failure defined as serum creatinine ≥ 3 milligrams per liter or requirement for renal replacement therapy despite adequate volume replacement

Respiratory failure defined as need for BIPAP therapy or ventilation

Circulatory failure defined as shock or requirement of vasopressor support to maintain mean arterial pressure ≥ 60 mm Hg despite adequate volume replacement

Multiple organ failure defined as failure ≥ 2 organs

Note: Sepsis will often be an SAE that precedes documented infection by 1-5 days. If sepsis is reported as an SAE and infection is never documented, then it should be classified separately, i.e., sepsis with documented infection or sepsis without documented infection.

Sepsis can be diagnosed by minor changes in lab parameters such as decrease in platelet count from 160,000 to 90,000 or increase in creatinine to 1.3 and drop in platelet count to 100-150,000 from normal on admission. However, these changes may also occur due to worsening liver disease without infection as a cause.

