17. Total WBC count $> 30,000/\text{mm}^3$
18. Known allergy or intolerance to therapeutic agents to be tested
19. Inability to voluntarily obtain informed consent from participant or guardian
20. Perceived inability to follow study procedures and comply with protocol
21. Platelet count $< 40,000 \text{ k/cumm.}$
22. Positive PCR test for COVID -19 within 7 days prior to the baseline day 0 visit*
23. Active gastrointestinal bleeding defined as hematemesis or melena with a decrease in hemoglobin more than 2 g/dl in 24 hrs. Due to gastrointestinal bleeding, or with a decrease in mean arterial BP to $< 65 \text{ mmHg}$

**Positive PCR test for COVID-19 is exclusionary only during screening period. If a patient tests positive any time after baseline randomization, a positive PCR test for COVID-19 will be considered as a SAE.*

The participants for this study will be recruited from a hospitalized population of participants meeting the eligibility criteria outlined above who live within one day travel from one of the

participating clinical centers and who have provided informed consent to participate in this clinical trial and who are willing to continue their participation for the anticipated follow-up period of the trial. Although the primary endpoint is survival at 90 days, follow-up visits will be continued up to 6 months.

Study Visits and Data Collection Schedule*****

	Screening	Treatment Phase							Follow-up phase
		D0	D3	D7	D14	D28	D60	D90	
Window (days)		±2	±2	±2	±2	±7	±7	±7	±7
Informed consent	x								
History and physical	x	x	x	x	x	x	x	x	x
Vital signs, weight ***	x	x	x	x	x	x	x	x	x
Alcohol consumption history	x	x			x	x	x	x	x
Randomization		x							
Concomitant medicines	x	x	x	x	x	x	x	x	x
Dispense Study Drug		x		*					
Adverse events			x	x	x	x	x	x	x
Electrocardiogram** ****	x								
Evaluation of compliance			x	x	x	x	x	x	
CBC, PT/INR, Hepatic Function Panel, BMP	x	x	x	x	x	x	x	x	x
Test for COVID-19****	x								
Sepsis studies, as indicated	x	x	x	x	x	x	x	x	x
Pregnancy test, serum**	x								
Pregnancy test, urine**		x			x	x	x	x	x
Blood collection for trough Anakinra levels		x	x	x	x				
Specimen Banking¶		x		x	x	x	x	x	x
Saliva Banking+		x						x	
Questionnaires δ	x					x	x	x	x

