8. History of other liver diseases including hepatitis B (positive HBsAg or HBV DNA), hepatitis C (positive HCV RNA), autoimmune hepatitis, Wilson disease, genetic hemochromatosis, alpha1-antitrypsin deficiency, or strong suspicion of Drug Induced Liver Injury (DILI). Previously treated hepatitis C that was cured (sustained virological response with negative RNA \geq 24 weeks following treatment) is not an exclusion.
9. History of HIV infection (positive HIV RNA or on treatment for HIV infection)
10. History or presence of cancer (including hepatocellular carcinoma) other than non-melanoma skin cancer
11. History of other significant medical problems such as autoimmune diseases, severe asthma, psoriasis, Inflammatory Bowel Disease (IBD), etc. that might require immunosuppressive treatments
12. Pregnancy or breastfeeding
13. Prior exposure to experimental therapies in last 3 months
14. Prior exposure to systemic corticosteroid (glucocorticoid) or immunosuppressive therapy for more than 4 days within previous 30 days
15. Need for inotropic pressor support to maintain perfusion to critical organs within prior 48 hours before randomization and initiation of experimental treatment
16. Clinically significant pancreatitis- abdominal pain, elevated lipase ($> 3 \times$ ULN) and at least edema of pancreas with fat-stranding on CT scan
17. Total WBC count $> 30,000/\text{mm}^3$
18. Known allergy or intolerance to therapeutic agents to be tested
19. Inability to voluntarily obtain informed consent from participant or guardian
20. Perceived inability to follow study procedures and comply with protocol
21. Platelet count $< 40,000 \text{ k/cumm.}$
22. Positive PCR test for COVID -19 within 7 days prior to the baseline day 0 visit*
23. Active gastrointestinal bleeding defined as hematemesis or melena with a decrease in hemoglobin more than 2 g/dl in 24 hrs. Due to gastrointestinal bleeding, or with a decrease in mean arterial BP to $< 65 \text{ mmHg}$.

**Positive PCR test for COVID-19 is exclusionary only during screening period. If a patient tests positive any time after baseline randomization, a positive PCR test for COVID-19 will be considered as a SAE.*

The participants for this study will be recruited from a hospitalized population of participants meeting the eligibility criteria outlined above who live within one day travel from one of the

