- 2) When to terminate the trial due to DILI concerns? The Data Safety Monitoring Committee (DSMB) should carefully monitor the number of discontinuations due to MELD/Child's Score worsening in the three treatment groups. Since this trial is not powered for rare adverse events, one should not look for statistically significant imbalance among treatment groups, but the DSMB should consider numerical imbalances that its members deem clinically significant. While it may be straight forward in some instances (for example, 2 discontinuations in group A but 5 discontinuations in group B) but in other instances it may not be as clear cut and one may continue the trial for a growing trend. In any case, the DSMB is advisory in nature and it makes a recommendation to the Sponsor which is the NIAAA for this trial. In addition to seeking the AlcHepNet Steering Committee input, the NIAAA may seek external input to assist in its deliberation if the DSMB recommends that the clinical trial must be terminated due to safety concerns.

Treatment holding/stopping rules for laboratory abnormalities

- If platelet counts drop to $< 40,000$ while on injectable study drugs, injectable study drugs will be held and resumed when platelet count is $\geq 40,000$.
- Worsening renal function

As all patients are randomized to treatment arms while hospitalized, the site's dispensing pharmacy will check the GFR before dispensing the study drugs for the day. Pharmacy will enter the daily lab values into a REDCap-based decision support form, which will aid the pharmacy by providing guidance on daily dispensation. This REDCap form is in addition to the pharmacy manual of procedures, which also provides guidance on daily dispensation. For weekend coverage, the GFR and platelet values from the Friday labs may be used to generate the dispensation schedule at some sites. If the subject's GFR has dropped to < 30 but ≥ 20 and the subject is in the anakinra group, Redcap will provide instructions for pharmacy to dose reduce to every other day by providing anakinra placebo one day, alternating with active anakinra the following day. If the GFR drops to < 20 mL/min, the instructions from REDCap will hold active anakinra and substitute with anakinra placebo

When the patient is discharged and now outpatient, all injectable drugs will be dose reduced and administered every other day when the GFR drops to < 30 but ≥ 20 mL/min. All injectable drugs

will be stopped if GFR drops to <20 mL/min.

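### The renal-failure creatinine threshold and the platelet exclusion are printed in units that conflict with the protocol's own figures

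*Combined protocol and SAP*

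**What the plan says.** **Creatinine.** Section 10.2.2 lists SAE classes common in severe alcoholic hepatitis. Its renal line sets renal failure at a serum creatinine of 3 or more "milligrams per liter or requirement for renal replacement therapy despite adequate volume replacement". The unit is written out in words. Earlier in the same list, one acute kidney injury (AKI) criterion is "Increase in creatinine of 0.3 mg/dl within a period of 48 hrs". The closing note of the section gives, as minor laboratory changes that can lead to a diagnosis of sepsis, a "decrease in platelet count from 160,000 to 90,000 or increase in creatinine to 1.3"; neither figure carries a unit. Renal failure is one of the organ failures that the list then combines: "Multiple organ failure defined as failure ≥ 2 organs".

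**Platelets.** Exclusion 21 is printed identically in the executive summary and in section 5.1: "Platelet count $< 40,000 \text{ k/cumm". The on-treatment rule in section 6.6.1 uses the number 40,000 with neither the k nor any unit: below it, "injectable study drugs will be held and resumed when platelet count is" at or above that same number.

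**The concern.** Both lines are operative text. One is an eligibility criterion; the other defines an organ failure that is reported as an SAE. Each should be applicable from the page by a site, a monitor or a programmer without guesswork, and neither is.

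The renal line reaches beyond its own SAE class because it counts toward multiple organ failure. Multi-organ failure is also listed as a secondary endpoint in the executive summary and in sections 3 and 8, and the protocol text defines it nowhere but section 10.2.2. If that definition is carried over to the endpoint, its unit matters there too.

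**Working it through.** The plan derives no figure here, so there is nothing to reproduce. The check converts each printed threshold and compares it with the protocol's other figures. Conversions: 1 mg/dl = 10 mg/L; 1 k/cumm = 1,000 per cumm.

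**Creatinine (all inputs from section 10.2.2)**

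1. Printed renal-failure level: 3 mg/L ÷ 10 = 0.3 mg/dl.
2. AKI rise: 0.3 mg/dl × 10 = 3 mg/L. One is a level and the other a change, so equal size is not in itself a contradiction. It has a consequence, though. A creatinine that has risen by 0.3 mg/dl must now be at least 0.3 mg/dl, so anyone who meets the 48-hour AKI criterion also reaches the printed renal-failure level. The two classes are then not separated by creatinine.
3. The minor change to 1.3, read in mg/dl as in the AKI line: 1.3 × 10 = 13 mg/L, and 13 ÷ 3 = 4.3 times the printed renal-failure level. Read in mg/L it would be 0.13 mg/dl, less than the AKI rise alone, so mg/dl is the natural reading.
4. The same number, 3, in mg/dl would be 30 mg/L, and 30 ÷ 3 = 10. This measures the gap only.
5. How many participants would be flagged cannot be computed, because the documents give no creatinine distribution. Under an assumed range of 0.4 to 2.0 mg/dl (4 to 20 mg/L), every value meets 3 mg/L; only values below 0.3 mg/dl would not.

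**Platelets (executive summary, sections 5.1, 6.6.1 and 10.2.2)**

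1. Printed exclusion: 40,000 k/cumm × 1,000 = 40,000,000 per cumm.
2. The same number without the k, as in section 6.6.1: 40,000,000 ÷ 40,000 = 1,000-fold apart.
3. Counts cited in section 10.2.2, read as per cumm:

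| Count | In k/cumm | 40,000 ÷ value | Below printed cut-off? |
|---|---|---|---|
| 90,000 | 90 | 444 | yes |
| 100,000 | 100 | 400 | yes |
| 150,000 | 150 | 267 | yes |
| 160,000 | 160 | 250 | yes |

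Every count the section mentions would be excluded as printed. Exclusion 17, in the same list, gives the white cell count as a plain number per cubic mm with no k.

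Neither item looks like a text-extraction fault: the creatinine unit is in words, and the platelet unit appears identically in two places.

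**The case against.** The strongest reply is that these are proofreading slips which the protocol's own numbers expose. A literal platelet criterion would stop enrolment at the first screening, so sites must be reading it otherwise. That is probably true and it limits the practical effect. It does not make the text right.

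A reader might infer more: that nearly every participant would be classed as in renal failure, that multi-organ failure would be inflated in both arms, and that a treatment difference would be diluted. The documents do not support this chain.

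- Neither the multi-organ failure endpoint nor exclusion 4 cites section 10.2.2. The link to the endpoint is plausible only because no other definition is given. The link to the exclusion is weaker still: the hepatic limb in 10.2.2 is a MELD rise on two consecutive occasions, which does not suit a one-time eligibility check.
- Renal eligibility has its own rule, a GFR limit in exclusion 5, and does not use the creatinine line.
- The separate organ-dysfunction endpoint rests on SOFA changes and on need for organ support, not on this cut.
- Section 10.2.1 leaves seriousness to the investigator's view, and no automated check of this creatinine threshold is described. The REDCap form in section 6.6.1 handles GFR and platelets for dispensing, and the platelet rule there is printed without the k.
- The phrase on volume replacement may qualify the creatinine limb as well as the dialysis limb, which would narrow literal flagging.
- The share flagged depends on an assumed creatinine range.

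All of these limits stand. What remains is the conflict in the printed units.

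**Conclusion.** Both thresholds are wrong as written, and the point is minor. The printed creatinine unit conflicts with the AKI unit and the 1.3 figure in its own section. The printed platelet unit conflicts with section 6.6.1 and with every platelet count cited in section 10.2.2. The conversion factors are exact. The comparison with 1.3 assumes mg/dl, and the comparison with the cited counts assumes per cumm, because the protocol prints no unit for either.

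The renal definition certainly feeds the multiple organ failure SAE class; that it feeds the secondary endpoint is possible but not stated. The primary endpoint, all-cause mortality to 90 days, uses neither threshold. The documents do not show that anyone was misclassified or wrongly excluded. No view is taken here on which clinical threshold is right.

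**What to change.** - Reconcile the creatinine unit within section 10.2.2, so that the renal-failure line, the AKI lines and the closing note each carry an explicit and consistent unit.
- Reconcile the platelet unit across exclusion 21 (executive summary and section 5.1) and the hold rule in section 6.6.1. Copying the unit from 6.6.1 is not enough, because that rule prints none.
- The sponsor should confirm the intended values in both cases.
- Check that any database check or endpoint definition using these thresholds carries the reconciled units. For multi-organ failure this means first establishing whether the endpoint uses the 10.2.2 definition.

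The cost is a few wording corrections, which can go into an amendment, and a short check of existing programs. No data are added, and the sample size and primary analysis do not change.

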10.2.3 Reporting SAEs

In agreeing to the provisions of this protocol, the investigator accepts all legal responsibilities for immediate reporting of SAEs to the study designated physician ([name] or his designee) as described below.

Table 4: Requirements for Reporting AEs to Various Stakeholders

	WIRB and Local IRB	NIAAA	DSMB	Other centers	Drug Company	FDA
AEs	Continuing Review	Annual Report	Every 6 months	DSMB reports (every 6 months)	DSMB reports (every 6 months)	Annual Report
TEAEs	Continuing Review	Annual Report	Every 6 months	DSMB reports (every 6 months)	DSMB reports (every 6 months)	Annual Report
SAEs	Continuing Review	2 working days	Every 6 months	DSMB reports (every 6 months)	DSMB reports (every 6 months)	Annual Report
SUSAR	5 days	2 working days	2 working days	2 working days	2 working days	7 days if death 15 days if other
Fatality	If unrelated Follow SAE timeline If related follow SUSAR timeline					

AE: Adverse Event; TEAS: Treatment Emergent Adverse Event; SAE: Serious Adverse Event; SUSAR: Serious Unsuspected Adverse Reaction; DSMB: Data and Safety Monitoring Board

The study designated physician for AlcHepNet - 02 is [name], who as the IND holder will assume the responsibility of monitoring safety concerns internally and serve as the liaison between the AlcHepNet and the DSMB.

All SAEs must be reported to the DCC-IU (i.e., within 2 working days) after the investigator identifies the SAE. SAEs should be entered into the REDCap system within 2 working days of the investigator becoming aware of the event. An initial report by telephone should then be followed, as soon as possible, by completion of the SAE CRF. Any supporting source documentation should be emailed to the assigned contact information as soon as possible. At a minimum the following information should be provided at the time of the initial report: 5-digit Study ID, a description of the event, at least one criterion classifying the event as Serious and the name and title of the reporting individual. Additionally, judgment of causality by the investigator must be provided as soon as possible to ensure timely reporting to regulatory authorities.

Following the initial report, any additional information obtained by the investigator about the SAE must be reported promptly to the DCC-IU.

The site investigator will assess whether the event is causally related to the study medication. The study designated physician ([name]) will consider the investigator's assessment, however, since [name] holds the IND and is primarily responsible for the overall safety of the participants, his causality assessment will take precedence over that of the site investigator. The study designated physician will determine if an SAE meets the criteria for an IND safety report (suspected, unexpected serious adverse reaction (SUSAR) in accordance with the FDA regulations, 312.32(c)(1)(i).

We will monitor safety closely, including all SAEs, AKI, and infection. We will provide unblinded data on SAEs including infections and AKI to the DSMB on monthly basis and hold the first DSMB after 3 months from the start of enrollment. We also propose a risk-based monitoring (RBM) approach which will create a more efficient and timely monitoring of accumulating data on the adverse events of interest, namely AKI and infections. The FDA has issued a final guidance in 2013 (Guidance for Industry. Oversight of Clinical Investigations — A Risk-Based Approach to Monitoring. August 2013) with a follow-up draft guidance in March 2019 (A Risk-Based Approach to Monitoring of Clinical Investigations. Questions and Answers. Guidance for Industry) that indicated the acceptability of RBM in studies with FDA oversight. While the details and implementation are left to the trial investigators, the overall concepts are included in these two documents – and in the Transcelerate RBM Position Paper (available at <https://www.transceleratebiopharmainc.com/wp-content/uploads/2013/10/TransCelarate-RBM-Position-Paper-FINAL-30MAY2013.pdf>). The essential elements of the study-specific AE/SAE monitoring plan would be for the RBM tools to interface with the main REDCap database so that any new AEs or SAEs would be immediately passed to the data driven RBM tools to determine if a trigger threshold has been reached. This interaction between receipt of data by REDCap and the comparison of the data to the triggers (and reporting of it on study dashboards) by the RBM tools will be virtually instantaneous. In addition, levels of thresholds can be set so that data trends of SAEs accumulating within treatment groups can be identified before significance is reached. **A complete monitoring plan, including RBM details, will be developed for review by the FDA and the DSMB within three months of study initiation.** We will also include Statistical Process Control (SPC) techniques in the monitoring plan to ensure that appropriate statistical controls are also utilized during the study.

10.2.3.1 Additional Principal Investigator Responsibilities for SAEs

The safety data recorded in the source document represent the official record of all AEs and SAEs reported in the trial. The investigator should comply with requests by the designated study physician to record the SAE on the participant's AE source document and, if necessary, provide a copy of this source document to the DCC-IU. Other supporting documents such as radiology reports, hospital discharge summaries and autopsy reports should also be provided, when appropriate, in anonymized fashion. Additionally, upon request by the designated study physician, the investigator should provide input into the SAE narrative and provide timely information to ensure prompt follow up and closure of the SAE report.

The investigator and supporting personnel responsible for participant care should discuss with the designated study physician any need for supplemental investigations of SAE(s). The results of these additional assessments must be reported to the designated study physician.

10.3 SAEs that are Anticipated to Occur in the Study Population (Expected SAEs)

Certain SAEs are anticipated to occur in this study population at some frequency independent of

drug exposure. Examples of these expected SAEs include variceal bleeding, ascites, spontaneous bacterial peritonitis, jaundice, hepatorenal syndrome, or hepatic encephalopathy. These expected SAEs as well as any related hospitalization will not be expeditiously reported as IND safety reports but will be reported in the manner described above (Table 4.). However, if an aggregate analysis indicates that these events are occurring more frequently in the drug treatment group than in a concurrent or historical control group, the SAEs will be reported as an IND safety report (21 CFR 312.32(c)(1)(c)). Follow up of AEs

All AEs, including clinically significant laboratory values or physical examination findings relative to pretreatment assessments, must be followed during the trial until the AE resolves, is no longer of clinical concern, has stabilized or is otherwise explained, or the participant is lost to follow up.

AEs ongoing at the final visit that are deemed to be ‘possibly, probably, or definitely’ related or of other clinical significance must be followed for as long as necessary to adequately evaluate the safety of the participant or until the event stabilizes, resolves, or is no longer of clinical concern. If resolved, a resolution date for the AE should be documented on the CRF. The investigator must ensure that follow up includes any supplemental investigations indicated to elucidate the nature and/or causality of the AE. This may include additional laboratory tests or investigations, or consultation with other healthcare professionals, as considered clinically appropriate by the investigator.

Note: Some SAEs like AKI, GI bleeding, infections, etc. can be both expected and common

